6.2.3 SCD PLACEMENT IN CRRT / ECMO CIRCUIT

Appendix M illustrates the integration of the CRRT circuit and SCD into the ECMO circuit. The CRRT return will be post pump.

Patients who receive CRRT on ECMO almost always develop their AKI, and hence their need for CRRT, after they have been on ECMO for at least 24 hours. Thus, the additional extracorporeal volume (ECV) associated with the CRRT circuit is not a factor, as the blood volume from ECMO is stable. In fact, the contribution of

the CRRT circuit is decreased (in terms of percent of ECV) since the ECMO circuit adds to the patient blood volume.

The pressure gradients are not an issue with CRRT on ECMO. In the most standard configurations, the CRRT circuit draws blood from the ECMO circuit post-pump and returns blood to the ECMO circuit pre-membrane, which is the safest configuration. The CRRT circuit will therefore see positive pressure from the ECMO circuit, and the current CRRT machines are designed to handle this. The CRRT pumps however, regulate the pressures within the CRRT circuit, so the SCD will see similar pressures compared to a non-ECMO situation.

6.3 BASELINE PERIOD

The Baseline Period begins at enrollment and ends at the start of the Observation Period. It is expected that the patient will begin the Observation Period before the patient has reached 12 hours of CRRT. The following information will be recorded as close to the start of the Observation Period as possible. Data from standard of care tests may be used as baseline data, as long as it is captured within the time frames noted.

- **Demographic Data**
 - a) Date of birth
 - b) Gender
 - c) Race/ethnicity
- **Hospitalization Data**
 - a) Hospital Admission Date
 - b) Hospital Admission Diagnosis
 - c) ICU Admission Date
 - d) ICU Admission Diagnosis
 - e) Medical History
- **Vital Signs/Physical Assessment (within 12 hours prior to the start of Observation Period unless otherwise indicated)**
 - Temperature
 - Blood Pressure, heart rate,
 - Body weight (within 24 hours if available)
 - PRISM II Score
 - Physical Exam
 - Urine Output (previous 24 hours)
 - ICU percent fluid overload at CRRT initiation (Defined as [(Fluid In (liters) – Fluid Out (liters))/ICU admission weight (kg)] x 100% where Fluid In and Fluid Out are calculated from ICU admission to CRRT initiation.
- **Clinical Laboratory Tests (within 12 hours prior to the start of Observation Period)**
 - CBC with differential
 - BUN/Creatinine
 - Na, K, Cl, HCO₃, Ca, Mg, Ionized Ca, PO₄
 - ALT, AST, Bilirubin, ALP, Total Protein, Albumin, Glucose
 - PT, PTT, INR
 - Urinalysis (if urine available)
- **Respiratory**
 - Status – Ventilator support (yes/no; date of intubation)
 - If on Vent: FiO₂
 - If on Vent with an arterial line: Arterial Blood Gas (12 hours prior to start of Observation Period)
 - If on Vent without an arterial line: Arterial Blood Gas (if available within 12 hours of start of Observation Period)
- **Blood for Research**
 - Blood sample will be sent to an outside laboratory for testing of biomarkers
- **Other (Event-driven)**
 - Acknowledgement (yes/no) to critical medications administered to the patient in the 24 hours prior to start of Observation Period
 - Adverse Events occurring since enrollment
 - Microbiology/culture data (within the last 72 hr.)

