5.3 EXCLUSION CRITERIA

1. Threshold blood pressure of 80/40 mmHg-- patients with both a systolic blood pressure of less than 80 mmHg and a diastolic blood pressure of less than 40 mmHg.
2. Irreversible brain damage based on available historical and clinical information.
3. Patients with a solid organ transplant or those with a bone marrow or stem cell transplant in the previous 100 days or who have not engrafted.
4. Acute or chronic use of circulatory support device, other than ECMO, such as LVADs, RVADs, BIVADs.
5. Presence of preexisting advanced chronic renal failure (i.e., ESRD) requiring chronic renal replacement therapy prior to this episode of acute kidney injury or with pre-existing chronic kidney disease (CKD) defined as a eGFR <30 ml/min/1.73m 2 . Patients who have never seen a pediatric nephrologist will be assumed not to have pre-existing CKD.
6. AKI occurring in the setting of burns, obstructive uropathy, vasculitis, scleroderma renal crisis, atheroembolism, functional or surgical nephrectomy, cyclosporine or tacrolimus nephrotoxicity.
7. Received >12 hour of CRRT (not including SCUF on ECMO) during this hospital admission or prior to transfer from an outside hospital.
8. Received >1 hemodialysis treatment during this hospital admission or prior to transfer from an outside hospital.
9. Metastatic malignancy which is actively being treated or may be treated by chemotherapy or radiation during the subsequent three month period after study therapy.
10. Chronic immunosuppression with the exception of corticosteroids up to a dose of 10 mg per day.
11. HIV or AIDS.
12. Severe chronic liver failure as determined by standard diagnostic requirements.

13. Current Do not Attempt Resuscitation (DNAR), Allow Natural Death (AND), or withdrawal of care status, or anticipated change in status within the next 7 days.
14. Patient not expected to survive 28 days because of an irreversible medical condition. (This is not restrictive to AKI, and may include situations such as the presence of irreversible brain damage, untreatable malignancy, inoperable life threatening condition, or any condition to which therapy is regarded as futile by the PI.)
15. Any medical condition that the Investigator thinks may interfere with the study objectives.
16. Physician refusal.
17. Dry weight <15 kg.
18. Platelet count <15,000/mm³.

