6.2.2 BLOOD CIRCUIT VOLUME

The additional blood volume for the SCD is 120 ml. This additional circuit blood volume for the standard SCD in >20 kg patients can be handled with blood priming with matched blood similar to the standard practice in neonates. Blood prime will occur if the total extracorporeal circuit volume (ECV) is greater than 10% of the patient's blood volume, based on an estimate of blood volume = 70 ml/kg x patient body weight (kg) [24]. The situation is most commonly encountered in neonatal CRRT, where circuit ECV can represent nearly 50% of patient blood volume, yet the same principles apply for this clinical study. [25]

Hypotension associated with blood priming can occur from transient dilution of vasoactive medications (e.g., norepinephrine), or from exposure to the hyperkalemic, hypocalcemic acidotic nature of blood banked blood, which can cause a bradykinin release syndrome (BRS) when the blood is exposed to the CRRT membrane. The BRS is usually associated with AN-69 membranes that will not be used in this study. Each center has its own blood priming protocol to mitigate the potential for this reaction. However, minimum standards for blood priming in this trial are detailed in Appendix L to ensure patient safety. [26]

Patients with AKI requiring CRRT are often hypotensive prior to initiation of CRRT. Initiation of CRRT itself can improve hemodynamics by correcting acidosis and hypocalcemia. Most patients with hemodynamic instability receive vasoactive medications. Since the age range and associated normal blood pressure parameters is wide for this pediatric study, it is difficult to mandate an age specific lower blood pressure threshold to preclude CRRT initiation, especially if CRRT can address the instability as noted above. However, a threshold BP of 80/40 mmHg-- patients with both a systolic blood pressure of less than 80 mmHg and a diastolic blood pressure of less than 40 mmHg will not be entered into the study.

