6.4 STUDY OBSERVATION PERIOD

The Study Observation Period begins when the patient starts treatment and will continue up to a maximum of 168 hours from the time of Observation Start. **Patient will begin the Observation Period before the patient has reached 12 hours on CRRT.** A patient may begin CRRT therapy and SCD treatment at the same time, which would also mark the beginning of the Study Observation Period.

This observation period has been broken into seven 24 hour time periods. It ends when the patient has reached 168 hours in the observation period or when the patient meets the termination criteria outlined in **Section 7.2** as determined by the Principal Investigator or Medical Team at the participating Clinical Site.

All tests are scheduled on a 24 hour cycle, or once a day, and can be scheduled to be drawn around each participating site's ICU blood drawing schedule, with the exception of any test that requires a specific draw frequency.

The following information will be obtained for patients enrolled during the study observation period on a daily basis unless otherwise specified:

- **Vital Signs/Physical Assessment**
 - Temperature
 - Blood Pressure , heart rate
 - Urine Output (previous 24 hours)
 - Net Fluid Balance (previous 24 hours)
- **Clinical Laboratory Tests**
 - CBC with differential – every 12 hours (+/- 4 hours)
 - BUN, Creatinine
 - Na, K, Cl, HCO₃, Ca, ionized Ca, Mg, PO₄
 - ALT, AST, Bilirubin, ALP, Total Protein, Albumin, Glucose
 - PT, PTT, INR
- **Respiratory**
 - Status – Ventilator support (yes/no; date of extubation)
 - If on Vent: FiO₂
 - If on Vent with an arterial line: Arterial Blood Gas
 - If on Vent without an arterial line: Arterial Blood Gas (if available)
- **Blood for Research**
 - Collect at hours 48, 96, 144, and end of study (+/- 4 hours). If study observation period ends prior to hour 168, collect at end of study observation period. Blood for biomarkers will be collected as close as possible to the time of SCD scheduled changes in the days required (+/- 4 hours) if practical.
 - Blood sample will be sent to an outside laboratory for testing of biomarkers

- **CRRT Parameters (Start at hour 0)**
 - Parameters include modality, blood flow rate, net fluid removal, dialysate or replacement solution flow rate, citrate infusion rate, calcium replacement rate.
 - System performance (circuit survival - event driven)
 - Post filter ionized calcium (+/- 1 hour)

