Besides the test of the hypothesis the study is focused on observable, empirical and laboratory determinations of patient safety while on the SCD. Previous human trials have been conducted on the SCD device and the protocol contains a review of AE and SAE data from all SCD human studies and findings from those studies contributed to constructing the investigative safety profile. Safety endpoint measures specified in the protocol include adverse events, laboratory safety parameters, vital signs, ventilation status and hemodynamic variables. Device integrity and performance measurements are also defined as are circumstances which demand premature termination of SCD treatment.

Prolonged exposure to the SCD is anticipated to result in superior outcomes, although as noted above, this pilot study is not designed to assess for efficacy. However, we understand that a minimum amount of exposure to the SCD will be required for an appropriate safety analysis and for making any inference regarding efficacy. The ppCRRT experience demonstrated that the majority of patients (201/370) received CRRT for 1 to 7 days and exhibited 65% survival (Symons et al CJASN 2007 Table7). Assuming our trial includes patients with similar illness severity, we have established a 72 minimum number of hours a patient will be treated with the SCD to be included in the final outcome analysis.

This trial is an early safety efficacy study but is not powered for statistical significance. Insights into a comparison of historical controls matched to SCD treated patients will utilize the ppCRRT Registry to match for: etiology of AKI, co-morbidities, CRRT modality, dose and form of anticoagulant, adverse events. [10].

The ppCRRT Registry has data fields for the primary reason for CRRT, including AKI and its cause, as well as co-morbidities which will be matched for primary organ system involvement. The CRRT modality was evenly distributed between convective and diffusive modality, with 60% of the convective modalities provided as CVVH and 40% as CVVHDF. The anticoagulant protocol will be standardized with ACD-A/CaCl₂ and all centers used the same protocol in ppCRRT Registry as outlined in this study protocol. Thus, the ppCRRT Registry dataset will be able to be matched to our study patient cohort. Also as noted above, patients will be matched for age, size and PRISM II score.

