The Prospective Pediatric CRRT (ppCRRT) database will be used as a control for the CRRT treatment related factors including: patient age, gender, primary cause of AKI, total treatment duration, CRRT modality (CVVH, CVVHD, CVVHDF), CRRT small solute clearance (ml/1.73m²/hour), baseline estimated GFR (using the original Schwartz formula, which was used in the ppCRRT), urine output in the 24 hours prior to CRRT initiation (ml/kg/hour), percent fluid overload at CRRT initiation based on admission ICU weight, vasoactive medication number at time of CRRT initiation and mean airway pressure at CRRT initiation.

An additional analysis will also evaluate patients who have achieved targeted iCa levels during 90% of treatment time and those who do not.

In summary this protocol meets all criteria necessary for clinical scientific inquiry related to a test of hypothesis in a well monitored environment focused on patient safety during the conduct of the study. Basic statistics will be performed on the data sets along with historical data comparisons and subjected to subset analysis where appropriate. The results will help to guide the design of a future pivotal study of this device.

The rational for therapy, study objectives and endpoints, design, inclusion and exclusion criteria are explicitly defined. Patient safety parameters are well documented including safety reporting, safety observations and assays, procedures for patient withdrawal and study discontinuation criteria along with monitoring device integrity and performance. Lastly, a review of all prior SCD human study safety data is included in the protocol for full disclosure to study investigators and the informed consent document includes a full description of all known and potential risks of the device treatment.

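### PRISM II, a matching variable for the registry comparison, is timed to SCD start rather than CRRT initiation, so up to 12 hours of prior CRRT may already have altered it in some patients

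*Combined protocol and SAP*

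**What the plan says.** Section 6.3 (Baseline Period) lists PRISM II under vital signs and physical assessment, with the window "within 12 hours prior to the start of Observation Period unless otherwise indicated". PRISM II has no time of its own. The general instruction for the list is "The following information will be recorded as close to the start of the Observation Period as possible". Appendix F shows a single PRISM II, in the Baseline column.

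The Observation Period starts with SCD treatment, and CRRT may already be running. Section 6.4 says "Patient will begin the Observation Period before the patient has reached 12 hours on CRRT" and also permits a simultaneous start. Exclusion 7 in Section 5.3 bars only patients who "Received >12 hour of CRRT (not including SCUF on ECMO) during this hospital admission" or before transfer.

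Section 11 uses the score in the historical comparison: "Also as noted above, patients will be matched for age, size and PRISM II score". It also lists factors to be controlled through the registry. Those with a stated time are urine output in the 24 hours before CRRT initiation, percent fluid overload at CRRT initiation, and "vasoactive medication number at time of CRRT initiation and mean airway pressure at CRRT initiation".

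On what early CRRT does, Section 6.2.2 says "Initiation of CRRT itself can improve hemodynamics by correcting acidosis and hypocalcemia".

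**The concern.** PRISM II is the only summary severity score named for matching. It is meant to describe how sick a child was before the treatments being compared. As timed, it describes a child who starts CRRT and SCD together on untreated values, and a child who starts SCD late in the permitted period on values that may follow many hours of CRRT. Two children equally sick when CRRT began could therefore be matched to different registry patients only because SCD was connected at different times.

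Mortality and dialysis dependency are to be compared with historical controls (Synopsis, Evaluation Plan). Section 10 plans an efficacy evaluation against those controls on 16 patients, and Section 11 says the results will guide a pivotal design. With so few patients, a handful of poor matches could change how the comparison reads.

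**Working it through.** The plan gives no figure on this point, so there is nothing to reproduce. The check sets the time rules side by side and sums the Appendix A points.

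**1. Where the score falls relative to CRRT initiation.** Let h be the hours of CRRT before SCD start, with 0 ≤ h < 12 (Section 6.4). The look-back is 12 hours (Section 6.3), so the part of the window before CRRT began is 12 − h hours.
- h = 0: 12 hours, so every value is untreated.
- h = 6: 6 hours.
- h = 11: 1 hour.

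Pre-CRRT values are never excluded, but the instruction to record close to SCD start favours the later ones. Following it places the score anywhere from 0 to almost 12 hours after CRRT began.

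**2. Time origin of the other factors.** Urine output, fluid overload, vasoactive number and mean airway pressure are all dated at or before CRRT initiation in Section 11. Fluid overload stands in the same Section 6.3 list as PRISM II and carries that anchor there too. PRISM II does not.

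**3. Points at stake (maximum per item, Appendix A).**
- All items: PaO2/FiO2 3 + PaCO2 5 + respiratory rate 5 + clotting 2 + bilirubin 6 + systolic 6 + diastolic 6 + heart rate 4 + coma score 6 + pupils 10 + potassium 5 + calcium 6 + glucose 8 + bicarbonate 3 = 75.
- Potassium, calcium, bicarbonate: 5 + 6 + 3 = 14, and 14/75 = 19%.
- With systolic pressure and heart rate: 14 + 6 + 4 = 24, and 24/75 = 32%.

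**4. Illustrations with assumed values (not expected shifts).**
- Chemistry only: potassium 6.8 (1) + calcium 7.5 (2) + bicarbonate 14 (3) = 6. After correction to 4.5, 9 and 22, the sum is 0.
- The same with systolic 72 (2) and heart rate 155 (4): 6 + 2 + 4 = 12. After correction, with systolic 90 and heart rate 140, the sum is 0.
- Opposite direction: potassium 5, calcium 9 and bicarbonate 20 score 0. If citrate CRRT moved them to 3.3 (1), 12.5 (6) and 33 (3), the sum is 10.

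**5. Average shift in the cohort.** Mean shift = f × d, where f is the share of patients with prior CRRT and d the mean drop among them. The documents give neither. Assuming f from 25% to 100% and d from 3 to 14 points, the range is 0.25 × 3 = 0.8 to 1.00 × 14 = 14 points. If everyone starts CRRT and SCD together, f = 0 and the shift is 0. The width of this range shows that the size cannot be determined from the documents.

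**The case against.** A reader might infer that trial patients as a group will look less sick than they were, and that the comparison is therefore biased against the device. The documents do not support that much, for four reasons.
- They do not say when the registry scored PRISM II, so the direction of any mismatch is conditional.
- CRRT can raise scored items as well as lower them. Section 6.2.1 foresees serum bicarbonate above 35, and Appendix A scores values above 32. Section 9.4 lists hypokalemia, hypo- or hypercalcemia, hypotension and arrhythmias as anticipated with CRRT or critical illness. Section 6.2.2 provides for hypotension at initiation.
- Nothing suggests that CRRT corrects the coma score, pupils, bilirubin or clotting times, so only part of the score is exposed.
- Simultaneous starters are unaffected, and several provisions read as if CRRT starts with SCD. Appendix D equates initiation of renal replacement therapy with the start of observation, and Appendix L primes one joint initial circuit for the smallest children.

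These four points stand, and they limit the claim.

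Three further objections have less force.
- Section 6.3 is a collection list and need not fix the matching time; its urine output item is dated differently from the one in Section 11. But the protocol schedules only one PRISM II, so that is the score available for matching.
- The covariates already anchored at CRRT initiation mitigate the problem in part. They do not repair a score that is itself a matching variable.
- Section 11 says the study is unpowered and not designed to assess efficacy. That lowers the stakes, but a systematic timing mismatch is not a matter of power.

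**Conclusion.** The point holds in a limited form. The timing rule lets PRISM II float from 0 to nearly 12 hours after CRRT initiation, while the other dated factors are fixed at or before it. The inconsistency is in the text and does not depend on any assumption. Its extent varies between patients with the length of prior CRRT, so no constant correction would remove it.

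In patients with prior CRRT, up to 24 of the 75 listed points are open to alteration, 14 of them from potassium, calcium and bicarbonate. These are ceilings, not expected shifts. A lowered score is the more likely direction given the plan's own description of early CRRT, but it is not certain. A bias against the device follows only if the score is lowered and the registry scored PRISM II at or before CRRT start. The latter is an assumption. The average effect cannot be estimated, because neither the share of patients with prior CRRT nor the change per patient is given.

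This is a worthwhile, inexpensive improvement to an exploratory comparison. It does not undermine the safety evaluation.

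**What to change.** - In Section 6.3 and Appendix F, define the PRISM II used for matching as scored from the last values before CRRT initiation, within a fixed window (for example, the 12 hours before CRRT start).
- In Section 11, state when PRISM II was scored in the registry, and use the same anchor on both sides where registry data allow. If they do not, say so as a limitation.
- Record hours of CRRT before SCD start for each patient. CRRT timing is already needed for exclusion 7 and the fluid-overload calculation, so this adds one derived field.
- Keep the vital signs and laboratory tests taken before SCD as the safety baseline.

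The change alters no treatment. Section 6.3 already accepts standard-of-care results as baseline data. The cost is retrospective abstraction for patients on CRRT before enrollment, including coma score, pupils, blood gas, bilirubin and clotting times. Some inputs may be missing for patients who started CRRT before transfer, so the plan should state how an incomplete score is handled in matching.

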6.4 STUDY OBSERVATION PERIOD

The Study Observation Period begins when the patient starts treatment and will continue up to a maximum of 168 hours from the time of Observation Start. **Patient will begin the Observation Period before the patient has reached 12 hours on CRRT.** A patient may begin CRRT therapy and SCD treatment at the same time, which would also mark the beginning of the Study Observation Period.

This observation period has been broken into seven 24 hour time periods. It ends when the patient has reached 168 hours in the observation period or when the patient meets the termination criteria outlined in **Section 7.2** as determined by the Principal Investigator or Medical Team at the participating Clinical Site.

All tests are scheduled on a 24 hour cycle, or once a day, and can be scheduled to be drawn around each participating site's ICU blood drawing schedule, with the exception of any test that requires a specific draw frequency.

The following information will be obtained for patients enrolled during the study observation period on a daily basis unless otherwise specified:

- **Vital Signs/Physical Assessment**
 - Temperature
 - Blood Pressure , heart rate
 - Urine Output (previous 24 hours)
 - Net Fluid Balance (previous 24 hours)
- **Clinical Laboratory Tests**
 - CBC with differential – every 12 hours (+/- 4 hours)
 - BUN, Creatinine
 - Na, K, Cl, HCO₃, Ca, ionized Ca, Mg, PO₄
 - ALT, AST, Bilirubin, ALP, Total Protein, Albumin, Glucose
 - PT, PTT, INR
- **Respiratory**
 - Status – Ventilator support (yes/no; date of extubation)
 - If on Vent: FiO₂
 - If on Vent with an arterial line: Arterial Blood Gas
 - If on Vent without an arterial line: Arterial Blood Gas (if available)
- **Blood for Research**
 - Collect at hours 48, 96, 144, and end of study (+/- 4 hours). If study observation period ends prior to hour 168, collect at end of study observation period. Blood for biomarkers will be collected as close as possible to the time of SCD scheduled changes in the days required (+/- 4 hours) if practical.
 - Blood sample will be sent to an outside laboratory for testing of biomarkers

- **CRRT Parameters (Start at hour 0)**
 - Parameters include modality, blood flow rate, net fluid removal, dialysate or replacement solution flow rate, citrate infusion rate, calcium replacement rate.
 - System performance (circuit survival - event driven)
 - Post filter ionized calcium (+/- 1 hour)

Therapy Initiation	Q 1 hr. until post filter iCa level <0.40 mmol/L; then Q 6hr.
After any Calcium or Citrate rate change	Q 1 hr. until post filter iCa level <0.40 mmol/L; then Q 6hr.
After any Interruption: Recirculation, Procedure, Restart	Q 1 hr. until post filter iCa level <0.40 mmol/L; then Q 6hr.

- **SCD Performance (Start at hour 0)**
 - SCD [REDACTED] performance (event driven)
 - SCD and SCD Blood Tubing Set Change every 24 hour (+/-4 hour)
- **Other (Event Driven)**
 - Acknowledgement (yes/no) to critical medications administered to the patient
 - Adverse Events
 - Diagnostic/Therapeutic Procedures
 - Microbiology/culture data

